Investigation (YCCI) will also be used for study recruitment, which includes dedicated recruitment staff, community outreach personnel, and the use of YCCI's Clinical Research at Yale website, www.yalestudies.org. The Program on Aging will also help with recruitment.

4. Assessment of Current Health Provider Relationship for HIPAA Consideration:

Does the Investigator or any member of the research team have a direct existing clinical relationship with any potential subject?

- Yes, all subjects
- Yes, some of the subjects
- No

If yes, describe the nature of this relationship.

Some of the participants may be patients of [name].

5. Request for waiver of HIPAA authorization: (When requesting a waiver of HIPAA Authorization for either the entire study, or for recruitment purposes only. Note: if you are collecting PHI as part of a phone or email screen, you must request a HIPAA waiver for recruitment purposes.)

Choose one:

- For entire study
- For recruitment/screening purposes only
- For inclusion of non-English speaking subject if short form is being used and there is no translated HIPAA research authorization form available on the University's HIPAA website at hipaa.yale.edu.

- i. Describe why it would be impracticable to obtain the subject's authorization for use/disclosure of this data:

With waiver of HIPAA authorization, databases can be accessed identify patients to contact about the study. Without the waiver, this rich source of potential subjects would not be available.

- ii. If requesting a waiver of **signed** authorization, describe why it would be impracticable to obtain the subject's signed authorization for use/disclosure of this data:

N/A

The investigator assures that the protected health information for which a Waiver of Authorization has been requested will not be reused or disclosed to any person or entity other than those listed in this application, except as required by law, for authorized oversight of this research study, or as specifically approved for use in another study by an IRB.

Researchers are reminded that unauthorized disclosures of PHI to individuals outside of the Yale HIPAA-Covered entity must be accounted for in the "accounting for disclosures log", by subject name,

purpose, date, recipients, and a description of information provided. Logs are to be forwarded to the Deputy HIPAA Privacy Officer.

- 6. Process of Consent/Assent:** Describe the setting and conditions under which consent/assent will be obtained, including parental permission or surrogate permission and the steps taken to ensure subjects' independent decision-making.

At the baseline visit at Yale School of Medicine, prior to signing the consent/assent document, the Principal Investigator or research assistant will provide subjects with additional information about the study and review the consent forms and other study-related documentation. All subjects participating in the study will provide written consent. All subjects will be informed of the option of not participating, or of stopping at any time during the interview.

- 7. Evaluation of Subject(s) Capacity to Provide Informed Consent/Assent:** Indicate how the personnel obtaining consent will assess the potential subject's ability and capacity to consent to the research being proposed.

The ability and capacity to consent/assent will be determined by the Principal Investigator or research assistant by thorough questioning during the process of consent. Potential subjects will be asked, "Could you explain to me what we are going to ask you to do in this study? This will help me be to be sure that you understand the research," as well as, "What more would you like to know about this study?"

- 8. Non-English Speaking Subjects:** Explain provisions in place to ensure comprehension for research involving non-English speaking subjects. If enrollment of these subjects is anticipated, translated copies of all consent materials must be submitted for approval prior to use.

Non-English speaking is part of the exclusion criteria for this study.

As a limited alternative to the above requirement, will you use the short form* for consenting process if you unexpectedly encounter a non-English speaking individual interested in study participation and the translation of the long form is not possible prior to intended enrollment?

YES NO

Note* If more than 2 study participants are enrolled using a short form translated into the same language, then the full consent form should be translated into that language for use the next time a subject speaking that language is to be enrolled.

Several translated short form templates are available on the HRPP website (yale.edu/hrpp) and translated HIPAA Research Authorization Forms are available on the HIPAA website (hipaa.yale.edu). If the translation of the short form is not available on our website, then the translated short form needs to be submitted to the IRB office for approval via modification prior to enrolling the subject. ***Please review the guidance and presentation on use of the short form available on the HRPP website.***

If using a short form without a translated HIPAA Research Authorization Form, please request a HIPAA waiver in the section above.

9. **Consent Waiver: In certain circumstances, the HIC may grant a waiver of signed consent, or a full waiver of consent, depending on the study.** If you will request either a waiver of consent, or a waiver of signed consent for this study, complete the appropriate section below.

Not Requesting any consent waivers

Requesting a waiver of signed consent:

Recruitment/Screening only

Entire Study (Note that an information sheet may be required.)

For a waiver of signed consent, address the following:

- Would the signed consent form be the only record linking the subject and the research?
YES **NO**
- Does a breach of confidentiality constitute the principal risk to subjects? **YES** **NO**

OR

- Does the research pose greater than minimal risk? **YES** **NO**
- Does the research include any activities that would require signed consent in a non-research context? **YES** **NO**

Requesting a waiver of consent:

Recruitment/Screening only

Entire Study

For a waiver of consent, please address the following:

- Does the research pose greater than minimal risk to subjects?
 Yes *If you answered yes, stop. A waiver cannot be granted.*
 No
- Will the waiver adversely affect subjects' rights and welfare? **YES** **NO**
- Why would the research be impracticable to conduct without the waiver? We will need to view medical records to determine eligibility before we call potential subjects
- Where appropriate, how will pertinent information be returned to, or shared with subjects at a later date? na

SECTION IV: PROTECTION OF RESEARCH SUBJECTS

Confidentiality & Security of Data:

- a. What protected health information (medical information along with the HIPAA identifiers) about subjects will be collected and used for the research?

Name, date of birth, telephone number, address, email address, sex, metabolic syndrome status, medications, other diagnoses. Only the PI and research assistant will have access to PHI.

- b. How will the research data be collected, recorded and stored?

The baseline, 8-week, and 3 month visits will entail data collection using validated questionnaires and self-report forms. These forms will be kept in paper form in each study participant's record and will be kept in a locked file cabinet at the Yale Center for Clinical Investigation. Only the PI and study assistant will have access to the participant's records. Forms will be coded with subject number; no personally identifiable information will be associated with these forms. Data will be entered to a secure OnCore database hosted at Yale University. OnCore is a secure, web-based application designed to support data capture for research studies, providing: 1) an intuitive interface for validated data entry; 2) audit trails for tracking data manipulation and export procedures; 3) automated export procedures for seamless data downloads to common statistical packages; and 4) procedures for importing data from external sources. The OnCore database will be supported by the Yale Center for Clinical Investigation/CTSA.

Incomplete or missing data prompts follow-up calls or electronic queries in OnCore. Our OnCore database will be checked for completeness in real-time from internal checks; while the PI and project manager will perform weekly audits for complete data.

We work closely with the Yale Program on Aging and the biostatistics core director, [name] [name], an expert in the design and analysis of clinical trials with older adults.

- c. How will the digital data be stored? CD DVD Flash Drive Portable Hard Drive Secured Server Laptop Computer Desktop Computer Other
- d. What methods and procedures will be used to safeguard the confidentiality and security of the identifiable study data and the storage media indicated above during and after the subject's participation in the study?

All documents and subject information will be strictly maintained according to HIC and HIPAA regulations to ensure confidentiality at all times. Access to subject information will be limited to a "need to know" basis and all data will be coded to maintain confidentiality. Only those investigators with appropriate Human Subjects training will have access to subject data. All electronic files are encrypted and password protected; paper files are kept in locked file cabinets. All data will be managed to assure strict confidentiality of subjects at all times.

All portable devices must contain encryption software, per University Policy 5100. If there is a technical reason a device cannot be encrypted please submit an exception request to the Information

Security, Policy and Compliance Office by clicking on url <http://its.yale.edu/egrc> or email [contact]

- e. What will be done with the data when the research is completed? Are there plans to destroy the identifiable data? If yes, describe how, by whom and when identifiers will be destroyed. If no, describe how the data and/or identifiers will be secured.

Data will be kept for five years after the study ends. Data will then be de-identified using a “Safe Harbor” (45CFR164.514(b)(2)) approach consistent with the HIPAA Privacy rule. De-identified data will be certified by a statistician that there is a very small risk that use of the protected health information could lead to a subject being identified. The principal investigator ([name]) is responsible for the implementation of data de-identification.

Any data, specimens, forms, reports, video recordings, and other records that leave the site will be identified only by a participant identification number (Participant ID, PID) to maintain confidentiality. All computer entry and networking programs will be done using PIDs only. Information will not be released without written permission of the participant, except as necessary for monitoring by IRB and the OHRP.

- f. Who will have access to the protected health information (such as the research sponsor, the investigator, the research staff, all research monitors, FDA, Yale Cancer Center Data and Safety Monitoring Committee (DSMC), SSC, etc.)? (please distinguish between PHI and de-identified data)

Only the principal investigator and research team will have access to PHI.

- g. If appropriate, has a [Certificate of Confidentiality](#) been obtained?

A Certificate of Confidentiality is not needed and therefore has not been obtained.

- h. Are any of the study procedures likely to yield information subject to mandatory reporting requirements? (e.g. HIV testing – reporting of communicable diseases; parent interview -incidents of child abuse, elderly abuse, etc.). Please verify to whom such instances will need to be reported.

No.

SECTION V: POTENTIAL BENEFITS

Potential Benefits: Identify any benefits that may be reasonably expected to result from the research, either to the subject(s) or to society at large. (Payment of subjects is not considered a benefit in this context of the risk benefit assessment.)

The potential improved patient satisfaction, functional status, and quality of life for older adults with metabolic syndrome can have far reaching implications, including greater receptivity to the benefits of interventions, superior adherence, and enhanced resiliency to the inevitable variations in chronic disease presentation. Adding MBSR to metabolic syndrome treatment regimens could provide tremendous benefit to the many older adults, in addition to relieving a sub-optimal and overburdened healthcare system. The relative risk to subjects participating in this pilot study is negligible. The greatest risk may be

that subjects are involved in alternative treatment that ultimately proves to be no more effective than the usual care they have already received. Thus, the risk-benefit ratio strongly favors the study participant.

The identification of a practical stress reduction regimen of that can produce symptomatic and psychological relief has the potential to help alleviate the suffering of patients with metabolic syndrome and improve public health. Results obtained from this initial line of inquiry will be the first step in developing a graduated, stepwise integrative medicine algorithm for the treatment of metabolic syndrome in older adults. The long-term intention is to expand this approach to a larger sample and to older couples with other types of medical risk factors.

SECTION VI: RESEARCH ALTERNATIVES AND ECONOMIC CONSIDERATIONS

1. **Alternatives:** What other alternatives are available to the study subjects outside of the research?

Alternatives to participating in the study would be to continue with their usual medical care, often involving pharmacotherapy.

2. **Payments for Participation (Economic Considerations):** Describe any payments that will be made to subjects, the amount and schedule of payments, and the conditions for receiving this compensation.

All payments will be made in the form of Visa[®] prepaid debit cards. As a thank you for their time, each participant will receive \$50 after completing the baseline assessment, \$50 after completing the 8-week assessment, and \$50 at 3 month follow-up, for a total of \$150.

3. **Costs for Participation (Economic Considerations):** Clearly describe the subject's costs associated with participation in the research, and the interventions or procedures of the study that will be provided at no cost to subjects.

Subjects will not incur any costs associated with participation in the research besides transportation fees. Parking stubs for the Doctor's Building parking lot are validated at each office visit and parking will be provided at the Social and Gerontology Health Laboratory at [name]. The MBSR intervention is provided at no cost to the subject.

4. **In Case of Injury:** This section is required for any research involving more than minimal risk, and for minimal risk research that presents the potential for physical harm (e.g., research involving blood draws).

This research does not involve more than minimal risk. There are no known risks associated with MBSR. Numerous clinical trials of MBSR have not reported significant adverse effects related to the intervention.

- b. Will medical treatment be available if research-related injury occurs?

The YCCI CSRU will provide this service.

c. Where and from whom may treatment be obtained?
The YCCI CSRU.

d. Are there any limits to the treatment being provided?

No.

e. Who will pay for this treatment?

The YCCI has liability for these circumstances.

f. How will the medical treatment be accessed by subjects?

The YCCI CSRU treatment will be available immediately if there is an injury.

References

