1. To determine the feasibility of Mindfulness Based Stress Reduction (MBSR) for older cohabiting, intimate couples in which one, or both partners, has metabolic syndrome. We will (a) monitor recruitment, (b) adherence, and (c) missing data for the intervention. We will explore how being a couple impacts the MBSR experience, assessing (a) the prevalence of both partners having metabolic syndrome versus one partner, (b) shared decision making about participation and adherence, (c) how MBSR can be tailored to the needs of older couples, and (d) the impact on relationship quality and shared health behaviors.

2. To determine whether MBSR improves self-reported physical health status (SF-36) (Ware Jr & Sherbourne, 1992) for each partner. Hypothesis 1: The intervention group will have a significantly greater score on the SF-12 scale than does the control group.

3. To determine if MBSR reduces perceived stress (Perceived Stress Scale (Roberti, Harrington, & Storch, 2006)) and increases mindfulness (Kentucky Inventory of Mindfulness Skills (Baer, Smith, & Allen, 2004)). Hypothesis 2: Perceived stress will be reduced and mindfulness will increase for the MBSR group compared to the control group.

4. Exploratory aim: To determine if an MBSR intervention is associated with decreases in the composite measure of metabolic syndrome (blood pressure, waist circumference, glucose levels, cholesterol, triglycerides) for each partner. Hypothesis 3: The metabolic syndrome composite score for partners will be smaller at the end of the study in the MBSR group compared to the control group.

2. Background:

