Metabolic syndrome is a common multifactorial disorder that increases risk for cardiovascular disease and diabetes and affects a substantial proportion of older adults(Eckel, Grundy, & Zimmet). Between 23 and 55% of older adults meet metabolic syndrome criteria, which consists of having three of the following: abdominal obesity, hypertriglyceridemia, low high-density lipoprotein (HDL) cholesterol, high blood pressure, and high fasting glucose (Denys et al., 2009). Although this is a common syndrome, there are few preventive interventions targeting metabolic syndrome (Dunkley et al., 2012). This is despite the fact that the NHLBI suggests that treatment start with lifestyle changes including diet, exercise, maintaining healthy weight, and stress reduction, with medications as a secondary treatment. With the increasing number of medications that older adults take (Charlesworth, Smit, Lee, Alramadhan, & Odden, 2015), lifestyle interventions are becoming even more important. To date, most lifestyle interventions target diet and exercise without explicitly addressing stress reduction. As stress is related to overall psychological and physical health as well as each metabolic syndrome biomarker (Matthews & Kuller, 2002), research on the efficacy of stress reduction interventions for older adults is critical.

Lifestyle interventions that target older couples may be more effective than lifestyle interventions that target older individuals. The majority of older adults (especially men) are in close, committed relationships (US Census Bureau). Within close relationships, especially older intimate cohabiting couples, partners' characteristics and environments make them similar not only in terms of stress, but also health behaviors and mental and physical health (Hoppmann, Michalowski, & Gerstorf, 2016). Partners also have important positive and negative influences on each other. By targeting both partners within a couple, lifestyle interventions have the capability of maximizing the positive influences and minimizing the negative influences. There is some preliminary evidence that this is the case, as multiple weight control interventions show added benefit of involving relationship partners in their programs (Black, Gleser, & Kooyers, 1990).

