Importantly, we will explore the dyadic effects of couple members' simultaneous engagement in the MBSR intervention. In addition to using proper statistical techniques to understand the effects of MBSR on each partner's outcomes, we will examine partner influences. For each primary hypothesis, we will examine the secondary hypothesis that each partner's improvement in each health outcome (self-report physical health, stress, mindfulness, and metabolic syndrome composite biomarker score) will be associated with improvement in the other partner's health outcome. In addition, we will examine the effects of the intervention on both partners' relationship satisfaction. Showing that relationship satisfaction can be enhanced is an important goal on its own, but we may also find that health outcomes improve when relationship quality improves.

3. Research Plan:

Procedures

Forty couples (N=80) will participate in a baseline visit to have blood drawn, BMI and BP measured, and to complete questionnaires assessing demographics, contextual factors, and baseline primary outcomes. Couples will be randomized to the MBSR condition (n=20 couples/ 40 individuals) or the wait list control condition (n=20 couples). The baseline blood draws and survey administration will take place at the CSRU, with the HRU as back up as needed. The blood analysis will be done by the YCCI Core lab. All participants will receive an informational sheet about metabolic syndrome.

Participants will be randomized to the intervention or wait-list group after informed consent is obtained, the initial blood is drawn and survey baseline is completed at the CSRU. A random digit generator will be used that assigns a condition (in this case, intervention or wait list) to each couple ID number.

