Feasibility outcomes will be observed, recorded, and qualitatively evaluated. Descriptive characteristics of the cohort will be summarized with means and standard deviations and counts and percentages according to intervention group. Although this pilot study will not be powered to test all outcomes for statistical significance, the primary quantitative outcomes are expected to have continuous Gaussian distributions making possible the comparison of intervention and control group results with linear mixed effects regression models that can accommodate the clustering of outcome results within couples. Finally, in anticipation of future studies of the metabolic syndrome outcome,

selected analyses will be conducted to compare the utility of the composite metabolic syndrome outcome and with a version of this outcome yielded by a measurement model in a structural equation modeling context.

Hypothesis 1: Self-reported physical health will be greater on average for participants in the MBSR intervention group compared to a wait-list control group. A multivariable linear mixed effects model will be used to assess whether self-reported physical health is greater in the intervention group than in the control group. A random effect will be used to account for the clustering of outcome values within couples. A pre-specified set of covariates will be entered into the regression model including baseline self-reported physical health and demographics and contextual factors that differ significantly across intervention and control groups. Model goodness of fit will be assessed with residual analysis, influence statistics, and goodness-of-fit statistics.

Hypothesis 2: MBSR will reduce each partner's self-reported stress and increase their mindfulness. The analyses for these two secondary outcomes will proceed according to the same procedures as cited for Hypothesis 1 above.

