Hypothesis 3: The metabolic syndrome composite score for participants will be smaller at the end of the study in the MBSR group compared to the control group. Given the exploratory nature of this hypothesis and the lack of consensus as to how to code a variable for metabolic syndrome, this Hypothesis 3 will be analyzed in three different ways: 1) with the outcome as a binary indicator variable indicating the occurrence of 3 or more of the 5 syndrome components; 2) with the outcome as a continuous variable obtained from the summation of Z-score transformations of the 5 syndrome components; and 3) as continuous latent factor or principal component construct obtained from a factor analytic measurement model. Performing these three analyses will provide invaluable insights for determining how the metabolic syndrome outcome will be coded in future studies using older samples.

We will explore the dyadic effects of couple members' simultaneous engagement in the MBSR intervention. In addition to the above analyses, we will use SPSS mixed models for analyzing repeated measures in couples. In this analytic approach, reports of health (primary outcome) (Level 1) are nested within time-invariant individual and couple variables (i.e., background variables, intervention condition (primary predictor), and moderators) at Level 2. The program allows for the analysis of intercepts and slopes of the hypothesized associations between Level 1 variables (i.e., within-couple relations between each partner's health) across all assessment points (baseline, 8 weeks, and 3 months), as well as interactions between Level 2 variables and Level 1 intercepts and slopes. In other words, we will assess whether the intervention was successful at the couple level by looking at the overall intervention effect, as well examine, for heterosexual couples, differential effects for husbands and wives by looking at the role (husband or wife) X intervention interaction.

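### The dyadic hypothesis is worded as a bare association between partners' improvements, which couple similarity alone could satisfy; it needs a contrast with the wait-list couples

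*Protocol*

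**What the plan says.** The last paragraph of the Background (Protocol, Section I, item 2) gives the purpose: "we will explore the dyadic effects of couple members' simultaneous engagement in the MBSR intervention". It speaks of examining partner influences. The hypothesis attached to each primary hypothesis is that one partner's improvement "will be associated with improvement in the other partner's health outcome". It covers four outcomes: self-reported physical health, stress, mindfulness and the metabolic composite. No arm is mentioned.

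Earlier in the same item, the protocol says of older cohabiting couples that "partners' characteristics and environments make them similar not only in terms of stress, but also health behaviors and mental and physical health".

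The Research Plan (item 3, Procedures) randomizes 40 couples as units, 20 to MBSR and 20 to the wait list. Both partners are always in the same arm, and no arm has one partner attending alone. Wait-list couples complete the same measures at the same time points.

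Statistical Considerations (item 13) describes two models:
- For Hypothesis 1: "A random effect will be used to account for the clustering of outcome values within couples". This effect is not tied to arm.
- For the dyadic analysis, a mixed model over baseline, 8 weeks and 3 months. Level 1 holds the "within-couple relations between each partner's health", intervention condition is the primary predictor at Level 2, and the software is said to allow interactions of Level 2 variables with Level 1 slopes. The summary sentence then reads "we will assess whether the intervention was successful at the couple level by looking at the overall intervention effect" and adds a role by intervention interaction for heterosexual couples.

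**The concern.** The hypothesis does not match its purpose. An association between partners' improvements can arise in at least three ways that involve no partner influence through MBSR:
- ordinary resemblance between people who live together, which would be present in wait-list couples too;
- each partner benefiting separately because both were assigned to MBSR, when arms are pooled;
- a shared class and instructor.

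Any of these satisfies the hypothesis as worded. The two tests that item 13 names do use the randomized arms, but neither asks whether the link between partners differs by arm.

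At stake is the interpretation of the dyadic results. Delivery to couples is the rationale of the study, and item 13 plans to use qualitative findings to explain the dyadic results in particular. A positive association could be taken as support for partner influence when the wait-list couples might show the same. The primary SF-12 comparison is not affected.

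**Working it through.** **Inputs.** 40 couples, 20 per arm (item 3, Procedures). Two-sided 0.05, borrowed from the Power paragraph of item 13, where it is set for the SF-12. The background correlation ρ between partners' changes is not given anywhere, so it is assumed: 0.1 to 0.4, with 0 as reference. The protocol has no power or correlation figure for the dyadic hypothesis, so there is none to reproduce; its one power figure concerns the SF-12 mean difference and is not used here.

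**Threshold.** With n = 40 couples and 38 degrees of freedom, t = 2.024. A correlation is significant when |r| exceeds t/√(df + t²) = 2.024/√(38 + 4.10) = 0.312.

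**Chance of a significant positive association with no MBSR effect on the partner link.** The Fisher z approximation is 1 − Φ(1.96 − atanh(ρ)·√(n − 3)), with √37 = 6.083:
- ρ = 0.1: 0.1003 × 6.083 = 0.610, giving 8.9%
- ρ = 0.2: 0.2027 × 6.083 = 1.233, giving 23.4%
- ρ = 0.3: 0.3095 × 6.083 = 1.883, giving 46.9%
- ρ = 0.4: 0.4236 × 6.083 = 2.577, giving 73.1%

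A simulation (10,000 trials per case, bivariate normal changes, the same ρ in both arms, no mean shift) agrees. The arm contrast is a two-sided Fisher z comparison of the two correlations.

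| ρ (assumed) | All 40 couples, positive | 20 MBSR couples only, positive | Arm contrast rejects |
|---|---|---|---|
| 0 | 2.6% | 2.5% | 5.1% |
| 0.1 | 8.4% | 5.8% | 4.7% |
| 0.2 | 23.3% | 13.3% | 5.0% |
| 0.3 | 47.2% | 25.2% | 4.9% |
| 0.4 | 74.5% | 43.4% | 5.0% |

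With 35 couples instead of 40, the pooled figures for ρ = 0.1 to 0.4 are 8.2%, 21.0%, 42.9% and 68.2%.

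**What the arm contrast can deliver.** With 20 couples per arm, the standard error of the difference in Fisher z is √(1/17 + 1/17) = 0.343.
- 0.2 against 0.5: (0.5493 − 0.2027)/0.343 = 1.01; power 1 − Φ(1.96 − 1.01) ≈ 17%
- 0.3 against 0.6: (0.6931 − 0.3095)/0.343 = 1.12; power ≈ 20%

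For one arm, an observed r of 0.3 in 20 couples has z limits 0.3095 ± 1.96/√17 = 0.3095 ± 0.475, a 95% interval for r of about −0.16 to 0.66.

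**The case against.** The strongest reply is that item 13 already contains the needed machinery. Condition is at Level 2, the partner-to-partner relation is at Level 1, and interactions between the levels are mentioned; condition by partner-association is one of them. Which term is fitted is often left to an SAP, and none is at hand. The aim is also exploratory, in a pilot that says it is not powered for every outcome.

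Much of this stands. A reader might infer that the protocol cannot use the wait-list couples as a reference for the partner association; the described model permits exactly that. What remains is that the protocol describes this as a capability, names two other tests, and never links the interaction to the hypothesis in the Background. The wording of that hypothesis is fixed in the protocol and is not an SAP detail.

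Two other strong readings also fail:
- That the hypothesis would be confirmed without any effect of MBSR. The protocol says partners are similar; it does not say their changes over weeks correlate, and it gives no value. At ρ of 0.1 to 0.3, most trials would not confirm it.
- That shared assignment inflates the association further. A uniform shift δ in both partners adds a correlation of (δ²/4)/(1 + δ²/4) if condition is ignored. With δ = 6.43/10 = 0.643 and ρ = 0, this is 0.1034/1.1034 = 0.094. But the planned dyadic model includes condition, which removes a uniform shift, so rates based on it do not describe the planned analysis. Background resemblance is not removed by a condition main effect.

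**Conclusion.** The point holds as a mismatch between one exploratory secondary hypothesis and its purpose. A positive partner association could come from couple similarity or separate benefit and would not by itself show partner influence through MBSR. With no MBSR effect on the partner link, it would appear in about 8%, 23%, 47% or 75% of trials at assumed background correlations of 0.1, 0.2, 0.3 or 0.4, against 2.6% at zero. These rates rest on assumed correlations, normal changes and 40 complete couples. Contrasting the association between arms keeps the error near 5% throughout that range.

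A reader might infer that this contrast would establish the value of attending as a couple. The design does not support that: no arm has one partner alone, and a stronger link in MBSR couples could also come from the shared class.

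**What to change.** In the Background and in item 13, restate the dyadic hypothesis: the association between partners' changes is stronger in MBSR couples than in wait-list couples. In the planned mixed model, fit the condition by partner-change term together with the condition main effect. Report the within-couple correlation of changes in each arm with its 95% confidence interval. Label the result exploratory. Describe any pooled or MBSR-only association as couple similarity, not partner influence. State that the trial cannot compare joint with individual MBSR.

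The cost is a reworded hypothesis and one named interaction term; no new data are needed. The price is precision: with 20 couples per arm the intervals are wide and power is low, so the result is an estimate for planning a later study and not a confirmation.
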